Eligibility Criteria: Patients 18 years of age and older presenting to the ED with acute musculoskeletal painful conditions (traumatic and non-traumatic) with an initial pain score of 5 on a standard 11- point (0 to 10) numeric rating scale. Patients will have to be awake, alert, and oriented to person, place, and time, and will be able to demonstrate understanding of the informed consent process and content. Patients also will have to demonstrate ability to verbalize the nature of any adverse effects they might experience as well as to express their pain severity by using the NRS.

Exclusion Criteria: Patients with altered mental status, allergy to aspirin and ketamine, pregnant patients, unstable vital signs (systolic blood pressure <90 or >180 mm Hg, pulse rate <50 or >150 beats/min, and respiration rate <10 or >30 breaths/min), inability to provide consent, consumption of Aspirin or NSAID's within 6 hours of arrival to the ED, active PUD, history of GI Hemorrhage,

history of renal and hepatic insufficiency, past medical history of alcohol or drug abuse, or schizophrenia.

Design: This is a prospective observational pilot trial evaluating analgesic efficacy and safety of VTS-K in adult patients presenting to the ED of Maimonides Medical Center with acute musculoskeletal painful conditions. Upon meeting the eligibility criteria, patients will be offered to participate in the study.

Data Collection Procedures: Each patient will be approached by a study investigator for acquisition of written informed consent and Health Insurance Portability and Accountability Act authorization after being evaluated by the treating emergency physician and determined to meet study eligibility criteria. When English will not be the participant's primary language, a language-appropriate consent form will be used and non-investigator, hospital-employed, trained interpreters or licensed telephone interpreter will assist in acquisition of informed consent. Baseline pain score will be determined with an 11-point numeric rating scale (0 to 10), described to the patient as "no pain" being 0 and "the worst pain imaginable" being 10. A study investigator will record the patient's body weight and baseline vital signs.

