The on-duty ED pharmacist will prepare an oral dose of ketamine by using a formulary for parenteral use. The oral dosing regimen of ketamine is 0.5 mg/kg that will be placed in the syringe or a medication cup. The research associate will deliver both medications (VTS-Aspirin and Oral Ketamine) to the patient. Study investigators will record pain scores and adverse effects at 15, 30, 60, and 90 minutes. If patients reported a pain numeric rating scale score of 5 or greater and requested additional pain relief, an oral immediate release morphine tablet of 7.5 mg will be given

All data will be recorded on data collection sheets, including patients' sex, demographics, medical history, and vital signs, and entered into SPSS (version 24.0; IBM Corp) by the research manager. Confirmation of written consent acquisition for all participants, and statistical analyses will be conducted by the statistician, who will work independently of any data collection.

Patients will be closely monitored for adverse effects during the entire study period (up to 90 minutes) by study investigators. Common adverse effects that are associated with oral ketamine are feeling of unreality, dizziness, nausea, vomiting, and sedation. Common adverse effects are associated with VTS-Aspirin are nausea, dyspepsia, epigastric discomfort.

Data Analysis: Data analyses will include frequency distributions and independent-sample t-test to assess differences in pain scores at the various intervals.

Mixed-model linear regression will be used to compare changes in pain numeric rating scale across time points. For categorical outcomes (eg, complete resolution of pain), a χ^2 or Fisher's exact test will be used to compare outcomes at 60 minutes. Based on the validation of a verbally administered rating scale of acute pain in the ED and the comparison of verbal and visual pain scales, we will use a primary outcome consisting of a minimal clinically meaningful difference of 1.3 between three groups at the 60-minute pain assessment.^{28,29}

Sample Size: Assuming a minimal clinically meaningful difference of 1.3 in change of pain score from the baseline until 60 minutes, given a standard deviation of 3.0, with a one-side 97.5%

confidence interval, we will need 21 subjects for this pilot trial. We would enroll 25 patients to account for any loss to follow-up.

References:

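### The plan claims to evaluate safety but schedules no vital signs after dosing and records sedation only as an ungraded adverse effect

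*Combined protocol and SAP*

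**What the plan says.** All of this is in the Study Design section of the combined protocol and SAP.

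- **Purpose (Design):** "This is a prospective observational pilot trial evaluating analgesic efficacy and safety of VTS-K". The Study Objectives, by contrast, name analgesic efficacy only.
- **Entry limits (Exclusion Criteria):** patients are excluded for "unstable vital signs (systolic blood pressure <90 or >180 mm Hg, pulse rate <50 or >150 beats/min, and respiration rate <10 or >30 breaths/min".
- **Before dosing (Data Collection Procedures):** "A study investigator will record the patient's body weight and baseline vital signs".
- **After dosing (Data Collection Procedures):** "Study investigators will record pain scores and adverse effects at 15, 30, 60, and 90 minutes".
- **Data sheets (same subsection):** "All data will be recorded on data collection sheets, including patients' sex, demographics, medical history, and vital signs". No time is given for any of these items.
- **Monitoring (same subsection):** "Patients will be closely monitored for adverse effects during the entire study period (up to 90 minutes) by study investigators". The next sentence reads: "Common adverse effects that are associated with oral ketamine are feeling of unreality, dizziness, nausea, vomiting, and sedation".
- **Data Analysis:** frequency distributions are mentioned in general terms. Every outcome that is named concerns pain, and no safety summary is described.

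**The concern.** The protocol regards three physiological measurements as important enough to keep a patient out of the trial, and takes vital signs at baseline. It then schedules no second reading, so there is nothing to compare the baseline with. Investigators can see or be told about most adverse effects, but a shift in blood pressure or pulse that causes no symptoms shows only if someone measures it. Rescue with oral morphine is also allowed, and no measurement is tied to it.

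What is at stake is the safety statement that the pilot can make. The Background presents VTS-K as an oral option with potentially fewer side effects and contrasts it with intravenous opioids, which it says need monitoring and equipment. A report of good tolerability would be read in that light, yet it would have no planned post-dose data on the measurements used for screening. With one treated group and no concurrent control described in the Design paragraph, change within each patient from baseline is the most informative physiological safety data that the trial could produce.

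**Working it through.** The plan gives no safety figure to reproduce. Its one calculated figure, the sample size, follows from (1.96 × 3.0 / 1.3)² = 20.46, rounded up to 21. It concerns the pain score and has no bearing here. The check is a reading of the text and a count.

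**1. What is measured, and when.**

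| Item | Baseline | 15 min | 30 min | 60 min | 90 min |
|---|---|---|---|---|---|
| Pain score | yes | yes | yes | yes | yes |
| Adverse effects | – | yes | yes | yes | yes |
| Vital signs | yes | not stated | not stated | not stated | not stated |
| Graded sedation | not stated | not stated | not stated | not stated | not stated |

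Vital signs are specified at 0 of 4 post-dose time points.

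**2. Number of occasions.** With 25 patients enrolled, 25 × 4 = 100 post-dose assessments are planned. With the 21 patients that the sample size requires, 21 × 4 = 84. None of these has a specified vital-sign reading. This counts occasions and does not estimate missed events.

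**3. The untimed data-sheet entry.** There are two possible readings.
- It refers to the baseline values, which fits its place beside sex, demographics and medical history. Then no post-dose vital signs are planned.
- It also covers post-dose values. Then their timing is left to whoever fills in the sheet. Readings taken only when someone is concerned have no consistent denominator and would miss changes without symptoms.

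On either reading, systematic post-dose capture is not specified.

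**4. Sedation.** Investigators monitor throughout, record adverse effects at four times, and have sedation named among the expected effects. Sedation can therefore be observed and recorded. What is missing is any definition or grading, so a briefly drowsy patient and a heavily sedated one could give the same entry.

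**5. The numeric limits.** They are stated as enrolment exclusions. The plan gives them no role after dosing. They can serve as ready-made reference values for a descriptive count, but the plan does not make crossing them after dosing a breach of any rule.

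**The case against.** The strongest defence is that safety is not the trial's stated objective. The title, objective, hypothesis and primary outcome all concern analgesia, and safety is claimed once, in the Design paragraph. The trial is a small pilot with investigators watching patients for up to 90 minutes and recording adverse effects four times. Listed effects such as vomiting and sedation are visible to an observer. The documents give no figure for blood-pressure, pulse or respiratory change after this treatment, so the number of changes missed is unknown and could be nil. The choice of a particular sedation scale is largely a matter of preference.

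Most of this stands, and it rules out two stronger inferences.

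- A reader might infer that detection depends on what patients can put into words, because the Eligibility Criteria say: "Patients also will have to demonstrate ability to verbalize the nature of any adverse effects they might experience". That is a condition of entry. The stated method is recording and monitoring by investigators, so it does not follow that sedation goes unmeasured or that a drowsy patient would leave no trace.
- A reader might infer that no vital signs are collected after dosing, or that the trial yields no objective safety data. The untimed data-sheet entry leaves post-dose recording open, and observed adverse effects are not merely self-report.

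The defence does not answer the remaining gap. Close monitoring for adverse effects names no measurement, and watching a patient does not reveal a symptom-free change in pressure or pulse. The word safety in the Design paragraph still needs data behind it.

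**Conclusion.** The point holds as a gap in planned safety measurement. As written, a trial that says it evaluates safety would not systematically capture a symptom-free post-dose change in the three measurements it screens on, and would record sedation only as an ungraded adverse effect. Its size is 0 of 4 post-dose time points, or none of 100 planned assessments, with specified vital signs. The clinical consequence cannot be quantified from the documents, and the efficacy analysis is not affected.

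This rests on two assumptions: that the baseline vital signs, which the plan does not itemise, include the three parameters in the Exclusion Criteria; and that no separate data-collection form sets post-dose times. If such a form exists, the remedy is to bring its schedule into the protocol.

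**What to change.** At the four existing assessments, record the same vital signs as at baseline, and have the investigator note observed sedation in one consistent way that is written down in advance. A named scale would do but is not essential. In Data Analysis, add a descriptive summary of change from baseline at each time point, the number of patients with any post-dose value outside the protocol's own enrolment limits, and the frequency of each adverse effect. Values should be marked as before or after rescue medication. The count against the limits is for description only and adds no clinical action rule.

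If vital signs are not added, state in the protocol that the data-sheet entry means baseline only, and limit the safety conclusion to investigator-recorded adverse effects.

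The cost is a few extra minutes at each assessment for staff who are already present, added data-sheet columns, and a sentence or two in the protocol and in Data Analysis. The drawback is slightly longer assessments.

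### No pre-dose symptom record is scheduled, so nausea or dizziness already present before VTS-K may enter the adverse-effect rate and cannot be reliably told apart at 15 minutes

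*Combined protocol and SAP*

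**What the plan says.** All references are to the combined protocol and SAP.

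- **Aim and design (Design).** "This is a prospective observational pilot trial evaluating analgesic efficacy and safety of VTS-K in adult patients". Every patient described receives VTS-K, and no other group or treatment is defined.
- **Before dosing (Data Collection Procedures).** A baseline pain score is taken on the 11-point scale. Then: "A study investigator will record the patient's body weight and baseline vital signs". For the data sheets: "All data will be recorded on data collection sheets, including patients' sex, demographics, medical history, and vital signs". Current symptoms are not named in any of these places.
- **After dosing (Data Collection Procedures).** "Study investigators will record pain scores and adverse effects at 15, 30, 60, and 90 minutes". Also: "Patients will be closely monitored for adverse effects during the entire study period (up to 90 minutes) by study investigators".
- **Expected effects (Data Collection Procedures).** For ketamine: "Common adverse effects that are associated with oral ketamine are feeling of unreality, dizziness, nausea, vomiting, and sedation". For the aspirin component: "Common adverse effects are associated with VTS-Aspirin are nausea, dyspepsia, epigastric discomfort".

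The plan does not define an adverse effect (for example, as new or worsened). It sets no severity grade and no causality rule, and it specifies no adverse-effect analysis.

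**The concern.** Pain is measured before and after dosing; symptoms have a schedule only after it. Patients enter with acute traumatic or non-traumatic pain scored 5 or more, and some may arrive nauseated or dizzy. Both symptoms are on the expected-effects list, and both are non-specific.

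A controlled trial would show the background rate of such symptoms in the control arm. Here no control treatment is described, so that background has to come from the patient's own state before VTS-K. If it is not written down before dosing, it cannot be reliably reconstructed later. At stake is how the safety description can be read: a crude post-dose proportion would mix new symptoms with ones the patient brought in, in unknown shares.

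**Working it through.** **Step 1. Is this a one-cohort design?** Sample Size gives a difference of 1.3, a standard deviation of 3.0 and a one-sided 97.5% confidence interval. The one-group precision formula is

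n = (z × SD / difference)² = (1.960 × 3.0 / 1.3)² = 20.46, rounded up to 21.

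This matches the stated 21. Enrolling 25 allows for 1 − 21/25 = 16% loss. The arithmetic fits a single cohort, as the Design paragraph describes. Data Analysis, however, plans an independent-sample t-test and refers to three groups. No such groups are defined, and these places need to be reconciled.

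**Step 2. What can the schedule separate?**

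- Absent at 15 minutes, present at 30, 60 or 90: the records show that the symptom arose after dosing. No baseline is needed.
- Present at 15 minutes: it may be new or may have been there before. The scheduled records do not say which.
- Present before dosing and then worse: this cannot be shown without a severity grade, and none is planned at any time.

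**Step 3. Which symptoms are exposed?** Patients must be awake and fully oriented, and altered mental status and schizophrenia are excluded, which limits prior sedation and probably feelings of unreality. Excluding active peptic ulcer disease, past gastrointestinal bleeding and recent aspirin or NSAID use probably removes some dyspepsia. No criterion removes a patient who is nauseated or dizzy on arrival.

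**Step 4. How large could the effect be?** The documents give no prevalence of pre-dose symptoms and no adverse-effect rate, so both are assumed here. Let b be the proportion with a listed symptom before dosing that persists and is recorded, and q the true proportion with a new effect, independent of b.

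- Expected patients affected = 25 × b
- Chance of at least one = 1 − (1 − b)^25
- Crude post-dose proportion = b + (1 − b) × q
- Excess over q = b × (1 − q)

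| b (assumed) | Patients of 25 | Chance of at least one | Excess, q = 0 (ceiling) | Crude rate, q = 10% | Excess, q = 10% | Excess, q = 50% |
|---|---|---|---|---|---|---|
| 5% | 1.25 | 72% | 5 points | 14.5% | 4.5 points | 2.5 points |
| 10% | 2.5 | 93% | 10 points | 19% | 9 points | 5 points |
| 20% | 5.0 | 99.6% | 20 points | 28% | 18 points | 10 points |

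In whole patients this is about 1 to 5 of 25. One patient is 1/25 = 4 points and five are 20 points. With 21 evaluable patients the expected counts are 1.05 to 4.2.

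**The case against.** **The plan states no attribution rule.** A reader might infer that every symptom present before dosing will be reported as caused by VTS-K. The documents do not say so. They say only that adverse effects are recorded, and Eligibility Criteria requires patients to be able to describe any they experience, so a patient could say that a symptom came first. This stands, and it limits the point to what may be counted and cannot be reliably separated. It does not remove the point: an investigator's unwritten discounting cannot be verified, may vary between investigators, and could also hide a real worsening.

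**The data are not wholly silent.** A reader might also infer that nothing would permit later correction. That goes too far. The treating physician evaluates each patient before consent, medical history is recorded, the data-sheet list is not exhaustive, and symptoms that begin after the 15-minute record are identifiable as new. All of this stands. None of it is a pre-dose record of the same symptoms, so the ambiguity at 15 minutes remains.

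**The size is assumed.** The ceiling requires every prior symptom to persist and be recorded, with no affected patient developing a new effect as well. The table shows how overlap shrinks the excess.

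**The hope of fewer side effects is a separate matter.** One might think the missing baseline is what prevents the Background's expectation of reduced side effects from being examined. That expectation is comparative, set against IV opioids, and one cohort cannot test it with or without a baseline.

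**Little depends on the rate.** The objective, hypothesis and primary outcome concern analgesia, and no safety threshold or test is planned. This stands and lowers the severity. The Design paragraph does, however, name safety as something the trial evaluates.

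**Conclusion.** The point holds in a limited form. Scheduled symptom recording starts at 15 minutes and no pre-dose symptom record is listed. With only VTS-K-treated patients described, prior nausea or dizziness may be counted as an adverse effect, and when present at 15 minutes it cannot be reliably distinguished from a new one. Counted that way, it would bias the descriptive adverse-effect rate upward.

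The range of about 1 to 5 of 25 patients is an upper limit for an assumed prevalence of 5% to 20%; the true figure is unknown. The 60-minute pain outcome is not affected. Rescue morphine within the 90 minutes is a second source of ambiguity in the same rate. Minor severity; a cheap improvement worth making before enrolment.

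**What to change.** 1. At time 0, with the baseline pain score and before VTS-K is given, record each symptom the protocol names, with a simple severity grade.
2. Use the same graded checklist at 15, 30, 60 and 90 minutes. Presence alone cannot show worsening, so the grade is needed at every time point.
3. State in the protocol that a symptom counts as treatment-emergent only if it is new or worse than at time 0.
4. Report treatment-emergent symptoms arising before and after rescue medication separately. This needs the time of any rescue dose on the data sheet, an item the listed data do not name.
5. Reconcile the reference to three groups in Data Analysis with the single cohort in Design and Sample Size.

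The cost is about a minute per patient at baseline, a severity field at each time point, a rescue-time field, a short protocol addition and slightly more analysis work. No extra visit is needed, and the sample size stays at 21 evaluable and 25 enrolled.

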An oral combination drug of VTS-Aspirin and ketamine (VTS-K) would facilitate the shift from IV opioids to a non-IV therapy for patients presenting to the ED with acute MSK pain. This formulation has a potential to provide effective analgesia in the ED with reduced side effects. VTS-K's proprietary oral formulation of established, safe, and well-understood APIs, makes it uniquely appropriate for use in the ED. VTS-K is administered orally, which is suitable for resource-poor environments in which the healthcare setting may be inadequate as well as suitable to improve the throughput of ED Patients by reducing their length of stay. This is especially pertinent given the alternative of IV opioids for pain management of acute MSK pain, which requires both clinical monitoring and equipment, whereas VTS-K promotes weaning off opioids, alleviating the resource consumption.

STUDY OBJECTIVES

To evaluate analgesic efficacy of orally administered VTS-K (liquid oral ketamine taken simultaneously with VTS-Aspirin and oral ketamine (in a liquid form)) for pain management of adult ED patients presenting to the ED with acute musculoskeletal pain

HYPOTHESIS

In our pilot study we hypothesize that the VTS-K combination will result in analgesia with a change in pain score at least of 1.3 points on NRS. The primary outcome of this trial is the reduction in participant's pain scores at 60 minutes post medication administration.

STUDY DESIGN

Subjects: Patients 18 years of age and older presenting to the ED with acute musculoskeletal painful conditions (traumatic and non-traumatic) with an initial pain score of 5 or more on a standard 11- point (0 to 10) numeric rating scale and requiring oral analgesia as determined by the treating attending physician. Patients' screening and enrollment will be performed by study investigators and research assistants. All patients will be enrolled at various times of the day when study investigators will be available for patient enrollment and an ED pharmacist will be available for medication preparation

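### Adverse effects that arise after rescue morphine cannot be separated from those of VTS-K, because no recording of rescue time or event onset is planned

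*Combined protocol and SAP*

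**What the plan says.** All places are in the combined protocol and SAP.

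- **Study Design, Design paragraph.** The study is a "prospective observational pilot trial evaluating analgesic efficacy and safety of VTS-K in adult patients".
- **Study Objectives.** The objective names efficacy only: "To evaluate analgesic efficacy of orally administered VTS-K".
- **Data Collection Procedures, assessments.** "Study investigators will record pain scores and adverse effects at 15, 30, 60, and 90 minutes". The end of follow-up is the same for all patients: "Patients will be closely monitored for adverse effects during the entire study period (up to 90 minutes) by study investigators".
- **Data Collection Procedures, rescue.** "If patients reported a pain numeric rating scale score of 5 or greater and requested additional pain relief", then "an oral immediate release morphine tablet of 7.5 mg will be given". No earliest or latest time is given.
- **Data Collection Procedures, expected effects.** "Common adverse effects that are associated with oral ketamine are feeling of unreality, dizziness, nausea, vomiting, and sedation". A second list covers VTS-Aspirin. There is none for morphine.
- **Data Collection Procedures, data items.** Sex, demographics, medical history and vital signs are named. The time of rescue and the onset time of an adverse effect are not.
- **Data Analysis.** Frequency distributions are the only item that could apply to adverse effects. No rule covers events after rescue.

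**The concern.** A patient who takes rescue morphine inside the window has had three drugs by the end of it. An adverse effect that first appears after the tablet may come from VTS-K, from morphine or from both. If all events to 90 minutes are counted together and labelled as VTS-K effects, some of that count belongs to the period with morphine, and the reader cannot tell how much.

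A control group might help to gauge this, but the Design paragraph and the Data Collection Procedures describe one regimen only. The Data Analysis section mentions three groups and an independent-sample t-test, yet nothing else in the document defines such groups. Without a described comparison, the frequencies themselves are the safety result.

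At stake is the interpretation of a descriptive safety table. The primary outcome, the planned tests and the sample size do not depend on it. What makes the point worth raising at the planning stage is that the two times may not be recoverable afterwards if they are not written down on the day.

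**Working it through.** **1. The plan's own figure.** The Sample Size section gives 21 evaluable patients, from a difference of 1.3, an SD of 3.0 and a one-sided 97.5% confidence limit. The one-sample precision formula reproduces it: (1.96 × 3.0 / 1.3)² = 20.46, rounded up to 21. The enrolment of 25 allows for 16% loss: 21 / (1 − 0.16) = 25. The number therefore rests on the pain score. For safety, 25 is simply the denominator.

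**2. Observation left after rescue.** This is 90 minus the time of rescue, shown here at the four assessment times:

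| Rescue at (min) | Observation after morphine (min) |
|---|---|
| 15 | 90 − 15 = 75 |
| 30 | 90 − 30 = 60 |
| 60 | 90 − 60 = 30 |
| 90 | 90 − 90 = 0 |

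Observation after VTS-K is 90 minutes in every row. Mixing needs rescue before 90 minutes. Rescue at 90 minutes causes no mixing but leaves no follow-up after morphine.

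**3. Could the planned data separate the events?** Four assessment times would allow a coarse split if the time of rescue were known. The plan does not say that it will be. Even then, take rescue between the 30- and 60-minute assessments and nausea first noted at 60 minutes: without an onset time, it cannot be placed before or after the tablet.

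**4. Size of the mixing.** Let p be the true proportion with a given effect from VTS-K, r the proportion rescued, and m the probability that morphine causes that effect within the window in a rescued patient who would otherwise not have had it. Assume p is the same in rescued and other patients. Then

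pooled proportion = p + r × m × (1 − p), and excess = r × m × (1 − p).

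The documents give none of the three inputs, so all are assumed. Excess in percentage points:

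| | r = 10% | r = 20% | r = 40% |
|---|---|---|---|
| p = 20%, m = 10% | 0.8 | 1.6 | 3.2 |
| p = 20%, m = 30% | 2.4 | 4.8 | 9.6 |
| p = 40%, m = 10% | 0.6 | 1.2 | 2.4 |
| p = 40%, m = 30% | 1.8 | 3.6 | 7.2 |

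The smallest value is 0.10 × 0.10 × 0.60 = 0.6 points and the largest is 0.40 × 0.30 × 0.80 = 9.6 points. Among 25 patients these are 0.15 and 2.4 patients.

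**5. Against sampling error.** The exact 95% interval is 6.8% to 40.7% for 5/25 and 21.1% to 61.3% for 10/25. The nearer limit lies 20 − 6.8 = 13.2 points away in the first case and 40 − 21.1 = 18.9 points in the second. The largest excess in the table is 9.6 points for p = 20% and 7.2 points for p = 40%, so both are smaller than those distances. Unlike sampling error, though, the excess always runs upward.

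**The case against.** The strongest reply is that safety carries little weight here. The objective and hypothesis concern pain, safety appears once as an aim, and no safety endpoint or threshold is set. In an uncontrolled pilot of 25, adverse effects cannot be firmly attributed to VTS-K even before rescue. This stands. It makes the point a cheap improvement and not a condition for running the trial.

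Second, the plan is silent; it does not prescribe pooling. Its list of data items is introduced as examples, so rescue time may be captured in practice. This also stands in part: a reader might infer that the sponsor intends to attribute every event to VTS-K, and the documents do not say so. They give no assurance of the opposite either.

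Third, counting all events to 90 minutes regardless of rescue is a defensible, conservative convention. Ending the VTS-K table at rescue would move later ketamine or aspirin effects out of it, and a patient rescued at 15 minutes would contribute only 15 minutes. This stands, and is why the all-events table should be kept.

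Two stronger readings are tempting and fail:

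- **That rescue cuts short the safety follow-up of VTS-K.** It does not. The 90-minute period is the same for every patient, and only the time observed after morphine varies. The documents do not claim to evaluate the safety of morphine or of the three drugs together.
- **That the plan is wrong to stop at 90 minutes.** No passage contradicts that period. Whether and how long to observe patients after rescue is a clinical decision for the sponsor and investigators.

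Finally, the documents list no morphine effects, so its overlap with nausea, vomiting, dizziness and sedation is an assumption here. The size in the working depends on it. The need to know which events followed a third drug does not.

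**Conclusion.** The point holds as a gap in data capture and reporting. The design claims a safety evaluation, rescue morphine can be given within the adverse-effect window, and nothing planned would let a reader separate events before it from events after it.

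The upward error in a reported frequency is about 0.6 to 9.6 points under the assumed ranges. The true size cannot be found from the documents, and it may well be smaller than the sampling error. It would be nil if nobody is rescued before 90 minutes. If rescued patients also differ in their underlying VTS-K risk, the simple formula no longer applies.

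The primary analysis and the enrolment of 25 are unaffected.

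**What to change.** 1. Add two fields to the data collection sheet: the clock time of rescue and the onset time of each adverse effect.
2. Keep the table of all events from dosing to 90 minutes. Beside it, report events before rescue, with the time observed, and events after rescue separately.
3. Limit the safety conclusion to the 90 minutes observed, and state that it does not cover any period after rescue beyond that.

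The cost is two data fields and one extra table. The drawback is that the pre-rescue table has shorter observation in rescued patients and may understate VTS-K effects if read alone, so it should stand next to the all-events table and not replace it. No change to the observation period or the rescue rule is proposed; those remain with the sponsor and investigators.

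### The primary outcome is written as a difference between three groups, but the trial treats one group and its outcome is a within-patient change

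*Combined protocol and SAP*

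**What the plan says.** The combined protocol and SAP describes the primary outcome in three places, and they do not agree.

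- **Hypothesis:** the primary outcome is the reduction in the participant's "pain scores at 60 minutes post medication administration", with a hypothesised change of at least 1.3 NRS points. No comparator is named.
- **Data Analysis:** the plan will use a "primary outcome consisting of a minimal clinically meaningful difference of 1.3 between three groups at the 60-minute pain assessment".
- **Sample Size:** the calculation rests on a "minimal clinically meaningful difference of 1.3 in change of pain score from the baseline until 60 minutes", an SD of 3.0 and a one-sided 97.5% confidence interval. It arrives at 21 subjects, with 25 enrolled to allow for loss to follow-up.

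On the number of groups, the Design paragraph says: "This is a prospective observational pilot trial evaluating analgesic efficacy and safety of VTS-K in adult patients presenting to the ED". Under Data Collection Procedures the research associate will "deliver both medications (VTS-Aspirin and Oral Ketamine) to the patient". No second regimen, control, randomisation or allocation is described.

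The methods listed under Data Analysis are frequency distributions, an "independent-sample t-test to assess differences in pain scores at the various intervals", a mixed model ("Mixed-model linear regression will be used to compare changes in pain numeric rating scale across time points") and, for categorical outcomes, a chi-square or Fisher's "exact test will be used to compare outcomes at 60 minutes". None is named as primary.

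**The concern.** A difference between three groups cannot be estimated when only one group exists. The independent-sample t-test and the chi-square or Fisher comparison likewise have no second group, and no subgroup comparison is stated that might supply one.

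The only way to apply the t-test to these data is between time points, for example baseline against 60 minutes. That treats two scores from the same patient as if they came from different people, so the standard error is wrong.

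At stake is the primary result. One of the two descriptions of the primary outcome cannot be carried out, the only t-test named does not suit the other, and no valid method is marked as primary. The choice is left to the analyst, possibly after the data are seen.

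**Working it through.** **Inputs from the Sample Size section:** difference d = 1.3; SD = 3.0; one-sided 97.5%, so z = 1.960; n = 21 evaluable, 25 enrolled. I read 3.0 as the SD of the change score. The sentence concerns change from baseline, but the plan does not say this outright.

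**1. Reproducing the stated 21.** One-group precision formula: n = (z × SD/d)² = (1.960 × 3.0/1.3)² = 20.46, rounded up to **21**. There is no power term. Other readings do not give 21:

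| Reading | n |
|---|---|
| One group, precision, z | 20.46 → 21 |
| One group, precision, t quantile | 23 |
| One group, one-sided 95% | 14.4 → 15 |
| One-sample test, 80% power (assumed) | 42 (z), 44 (t) |
| Difference between two groups, precision: 2 × 20.46 | 40.9 → 41 per group |

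At 41 per group, three groups would need 3 × 41 = 123 patients. The stated number was therefore built for one group.

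**2. Taking three groups literally.** With 21 patients split 7/7/7, the half-width for a pairwise difference is 1.960 × 3.0 × √(2/7) = 3.14, and 3.14/1.3 = 2.4 times the target difference.

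**3. Precision of the one-group mean change.** Half-width = quantile × 3.0/√n.

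| n | SE | z | t |
|---|---|---|---|
| 21 | 0.655 | 1.28 | 1.37 |
| 23 | 0.626 | 1.23 | 1.297 |
| 25 | 0.600 | 1.18 | 1.24 |

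With the t quantile, the half-width first falls below 1.3 at 23 patients.

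**4. Effect of ignoring the pairing at n = 21.** Hold the SD of change at 3.0. Assume a baseline SD s₀ and a correlation ρ between the two scores (neither is in the plan). Solve s₀² + s₁² − 2ρs₀s₁ = 9 for the 60-minute SD s₁. The unpaired half-width is then t(40) × √((s₀² + s₁²)/21), with t(40) = 2.021.

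| s₀ | ρ = 0 | ρ = 0.3 | ρ = 0.5 | ρ at which it equals 1.37 |
|---|---|---|---|---|
| 1.0 | 1.32 | 1.46 | 1.55 | 0.10 |
| 1.5 | 1.32 | 1.51 | 1.66 | 0.07 |
| 2.0 | 1.32 | 1.56 | 1.76 | 0.06 |

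The correct paired value is 1.37 throughout. The unpaired interval is too wide at moderate positive correlation and slightly too narrow near zero.

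**The case against.** The best defence is that the gap is narrower than it looks. The Hypothesis section already fixes the outcome, the time and the size of change, and the Sample Size section repeats them. The mixed model is a valid within-patient method and can supply the baseline-to-60-minute contrast. On that view the three-group phrase is a stray wording error in a 25-patient pilot, and any competent analyst would do the sensible thing.

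Part of this stands. The mixed model and the frequency distributions do fit one group, and a 60-minute contrast from the mixed model would also be a sound primary analysis. To say the analyst is left to choose after seeing the data is somewhat strong, since much is already fixed. But the plan neither specifies that contrast nor names any method as primary. Deleting the phrase alone would leave two tests with nothing to compare.

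It is also fair that the pairing figures are illustrative. The t-test sentence does not say which scores are compared, the SDs and correlations are assumed (they imply a 60-minute SD of about 2.9 to 3.5), and within the 0.3 to 0.5 range the error only widens the interval. The three-group sizes show what the plan was not sized for. The conclusion does not depend on any of these.

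Finally, restating the outcome does not settle whether the lower bound is to be compared with 0 or with 1.3. That is a real gap, but a separate one.

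**Conclusion.** The concern holds. The primary outcome in Data Analysis is wrong as written: it names a comparison that the design cannot provide and conflicts with the Hypothesis and Sample Size sections. The independent-sample t-test and the chi-square or Fisher comparison do not fit the design either. It should be corrected before any analysis.

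The strongest evidence is that 20.46 rounds up to the stated 21 under a one-group formula, while a between-group difference would need 41 per group. The single-group reading is an inference, since the plan never uses the term, but only the disputed phrase and tests point elsewhere. Reading 3.0 as the SD of change is also an inference. The pairing error, 1.46 to 1.76 against 1.37, holds only under the assumed SDs and correlations.

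**What to change.** 1. In Data Analysis, remove the reference to three groups and write: *The primary outcome is the mean within-patient reduction in NRS from baseline to 60 minutes in the single VTS-K group, reported with its one-sided 97.5% lower confidence bound.*
2. Replace the independent-sample t-test with a paired (one-sample) t analysis of change from baseline, named as primary, and keep the mixed model across time points as secondary. If the team prefers the mixed model as primary, the 60-minute contrast must be written out; the essential step is to name one within-patient method in advance.
3. Replace the chi-square or Fisher comparison with the 60-minute proportion and its confidence interval.
4. In Sample Size, state that 3.0 is the SD of change. Note that the calculation used z (half-width 1.28 at 21), while the t analysis gives 1.37 at 21 and 1.24 if all 25 are evaluable.

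Separately, state in advance whether the lower bound is to be compared with 0 or with 1.3.

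The cost is a few sentences. The 21 evaluable and 25 enrolled patients, the assessment times and the data collected stay the same.
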